# **Revision Control**

Protocol version	Updated SAP version number	Section number changed	Description of change	Date changed

# **Abbreviations and Definitions**

AAH, acute alcoholic hepatitis CRP, C-reactive protein HE, Hepatic encephalopathy HR, Hazard ratio HRS, Hepatorenal syndrome SBP, Spontaneous bacterial peritonitis IL-6, Interleukin 6 LPS, lipopolysaccharide mITT, modified intention to treat TIPS, Transjugular intrahepatic portosystemic shunt vWF, von Willebrand Factor

# Section 2: Introduction

### **Background and Rationale**

The natural history of cirrhosis is characterized by the frequent occurrence of infections. Spontaneous bacterial peritonitis (SBP), one of the most common infections, leads to a heavy-hospital mortality rate (20-30%) despite appropriate treatment. It is now well-acknowledged that intestinal bacterial translocation is a major mechanism in the development of SBP. Prevention of SBP remains challenging in severe cirrhotic patients with ascites. The recommendation of HAS of poorly absorbable antibiotics to decrease bacterial translocation, such as norfloxacin, is well-accepted for the secondary prophylaxis of SBP, but only one third of practitioners working in French hospitals routinely prescribe norfloxacin for the primary prophylaxis of SBP (Thevenot T, et al. Liver Int 2013;33:389-97.). Although recent guidelines (EASL CPG. J Hepatol 2018;69:406-60. Biggins SW, et al. Hepatology 2021;74:1014-48) recommends a primary prophylaxis of SBP to cirrhotic patients with a low protein level in ascites (< 15 g/L) and a poor liver function or a fragile hemodynamic status (Fernández J, et al. Gastroenterology 2007;133:818-24), most French practitioners do not adhere to these guidelines probably because they are concerned with bacterial resistance associated with long-term use of norfloxacin. Moreover, the unique randomized trial assessing norfloxacin for the primary prophylaxis of SBP in severe cirrhotic patients had a small sample size (only 68 patients included) and the primary outcome (survival at 1 year) was at the limit of significance (p=0,05) mainly due to a loss of effectiveness of norfloxacin during the study period. A new strategy using a very poorly absorbed antibiotic without known major resistance (like rifaximin) could advantageously replace norfloxacin. The main purpose of this multicenter, double-blind, placebo-controlled randomized trial is to reduce the one-year

mortality rate by comparing two treatment strategies in "severe" cirrhotic patients with low protein level in ascites (< 15 g/L). Criteria of "severe" cirrhosis are the followings: 1) impaired renal function (serum creatinine  $\geq 106 \ \mu mol/L$ , uremia  $\geq 9 \ mmol/L$  or serum sodium  $\leq 130 \ mmol/L$ ) or 2) severe liver impairment (Child-Pugh score  $\geq 9$  with serum total bilirubin levels  $\geq 51 \ \mu mol/L$ ). The two proposed strategies will be to administer active or placebo rifaximin 550 mg x 2 / day for 12 months. Considering the probability of a noticeable survival benefit in the rifaximin arm, one interim analysis will be conducted, the significance boundaries being determined by a flexible alpha spending function. A total of 160 patients (80 per group) will permit to detect a 20% difference in the one-year mortality rate (60% in group with placebo versus 40% in the active rifaximin group), with a  $\beta$  error of 15% and a  $\alpha$  nominal inferior to 5% (2-tailed assumption) and considering that 10% of the patients may drop-out of the study follow-up. The inclusion period will be 48 months and 17 centers will participate.

### **Objectives**

**Primary objective**: To demonstrate the efficacy of rifaximin compared to placebo in reducing the risk of death at 12 months by primary prophylaxis of spontaneous ascites fluid in "severe" cirrhotic patients with high ascites containing low protein levels in ascites (< 15 g/L).

### Secondary objectives:

Demonstrate the effectiveness of rifaximin compared to placebo in reducing:

- Hospital mortality rate and mortality rate at 3 and 6 months
- Incidence of spontaneous ascites fluid infection at 12 months
- Incidence of other complications of cirrhosis (hepatorenal syndrome, gastrointestinal hemorrhage, hepatic encephalopathy) at 12 months
- Number of days spent in hospital during the follow-up period
- Analyze the safety of the drug under study
- Analyze the composition of the gut microbiota in 25 patients in each group (day 1, months 3, 6, 12 and 18).
- To show that rifaximin significantly decreases (compared to placebo) serum levels of IL-6, lipopolysaccharides (LPS), copeptin, von Willebrand factor antigen and CRP between J1 and J30.

# **Section 3: Study Methods**

# 3.1 Trial Design

Multicenter, double-blind, placebo-controlled randomized clinical trial,

Randomization in **two parallel groups** (group A: "active rifaximin" and group B: "rifaximin placebo") in a 1:1 ratio and stratification on the center.

One interim analysis according to an alpha spending function approach

### **Investigational product**

- Tablets for oral administration, containing either 550 mg of active rifaximin or rifaximin placebo
- Treatment phase [from Day 1 (post-randomization) to Study End Date]:

**Group A** (rifaximin 550 mg): twice daily administration of one tablet containing 550 mg of active rifaximin **Group B** (rifaximin placebo): twice daily administration of one rifaximin placebo tablet

### **3.2 Randomization**

All consecutive severe cirrhotic patients with large ascites who will be admitted to the participating centers will be screened for eligibility (see inclusion and exclusion criteria). After the patient signs the informed consent form, and after eligibility is documented based on inclusion / exclusion criteria mentioned above, the Investigator will connect to the CleanWeb web site (chrub.tentelemed.com/). For each new patient, the investigator will use the eCRF to include the patient into the study and the Interactive Web Response System

(IWRS) will affect a randomization arm to the patient. The IWRS center (INSERM CIC 1431, Besancon, France) will allocate treatment based on a pre-specified randomization list, generated by the data manager ([name]) of the study, using study center as a stratification parameter. A list of treatment kit numbers corresponding to each treatment arm will be centrally generated by LC2 Pharma Company ([name]. Contact: [name]) and the treatment kits will be prepared in accordance with this list. Numbers will not be reused regardless of the status of the use of the corresponding study drug. The randomization will be performed in a 1:1 ratio, the number of subjects per block, block sequences will only be known by the methodologist (Pr [name] and [name]) and the data manager of the study. The IWRS (INSERM CIC 1431, Besancon, France) randomizes the patient into one of the two study arms and affects a randomization number as well as a treatment kit number to the patient. The IWRS developed by INSERM CIC 1431 ensures that the randomization is confirmed by email to the investigator and to the sponsor. The IWRS enables the randomization of patients at any time of the day throughout the whole study period. A technical helpdesk will provide support to investigators by phone or email. A web demonstration will be carried out in each participating center. In addition, an instruction manual describing the randomization process performed by the IWRS will be provided by the Clinical Research Assistant of the sponsor of the study to each participating center.

All patients randomized by the IWRS are irrevocably enrolled in the study, whether or not they are subsequently found to be eligible or actually receive the allocated treatment. As a consequence, patients should be followed until their last visit, until stopping rules apply or death.

# 3.3 Sample size

The sample size is estimated based on a projected 40% survival rate at 12 months in the placebo group and 60% in the rifaximin group and a dropout rate of 10% at 12 months. In order to be able to detect any noticeable survival benefit in the rifaximin arm early in the trial, one interim analysis will be conducted. The significance boundaries of the interim and the final analyses were determined using a flexible alpha spending function (specifically alpha time (t2) spending function). This method ensures an alpha nominal risk inferior to 0.05 for the whole analysis.

We calculated that 160 patients (80 per group) would yield an 85% power in a two-sided test of hypothesis. The interim analysis will be performed when about 70% of the expected information is available (112 patients with complete follow-up), with a significance boundary p-value of 0.01. Consequently, the final analysis will have to be performed with a significance boundary p-value of 0.043. The estimated alpha nominal risk using these critical values will be 0.048. All sample size calculations were performed using PASS 14 software.

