# **Section 6: Analysis**

# **6.1 Outcome Definition**

### Primary endpoint

12-month survival. Death, whatever the recorded cause, will be considered as the primary endpoints. The date and, whenever possible, the causes of death will be recorded.

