# **6.2 Analysis Methods**

### Primary end-point analysis

The Kaplan Meier method will be used to estimate cumulative mortality rate over the 12-month follow-up. The survival rate will be compared using the log-rank test.

Hazard ratio for death (rifaximin group vs. control group) and its 95% confidence interval will be determined using a Cox proportional hazard model. In this model, a center effect will be tested as well as interaction between treatment and center. The assumption of proportional hazards will be tested using Schoenfeld residuals and if violated, the model will be fitted with a treatment- time interaction or a time-varying covariate, as appropriate.

The mortality rate at 12 months will be described according to age, sex, and specific liver scores (Child-Pugh and MELD) to examine their potential effects. Each of these factors will be analyzed statistically using a Cox proportional hazard model incorporating terms for treatment, the covariate and the treatment-by-covariate interaction.

The number of dead patients, estimated treatment effect hazard ratios, and associated 95% confidence intervals will be calculated within each of the subgroups generated by these analyses.

Covariate n	No. Deaths	Treatment effect HR - 95%CI	P value
Intervention			
Placebo		Ref	
Rifaxim		Treatment effect	
Subgroup analyses			
Age			
<median< td="">	<median effect<="" td="">	</median>	</median<>		<median effect<="" td="">	</median>	
>median		>median effect	—
Sex			
Male		Effect in men —	
Female	I AO	Effect in women	
Child Pugh score			
В		Effect in B patients —	
С		Effect in C patients —	
Child Pugh score		Â	
<median< td="">	<median effect="" td="" —<=""></median>	</median<>		<median effect="" td="" —<=""></median>	
>median		>median effect —	

Sensitivity analyses

Analysis of the primary endpoint will be repeated after exclusion of patients with a suspicion of AAH and a Maddrey score  $\geq$  32 points.

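### With 160 patients and a primary analysis limited to 12 months, power is about 70%, not the stated 85%

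*SAP*

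**What the plan says.** Section 3.3 bases the sample size on a "projected 40% survival rate at 12 months in the placebo group and 60% in the rifaximin group", with 10% dropout at 12 months. It concludes: "We calculated that 160 patients (80 per group) would yield an 85% power in a two-sided test of hypothesis". One interim analysis is planned at about 70% of the information, counted as 112 patients with complete follow-up. The boundaries are p = 0.01 at the interim and p = 0.043 at the end.

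The Background and Rationale in section 2 makes the same claim in terms of mortality: "A total of 160 patients (80 per group) will permit to detect a 20% difference in the one-year mortality rate", that is "60% in group with placebo versus 40% in the active rifaximin group", with a 15% type II error, a two-tailed alpha below 5% and 10% dropout.

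Section 6.1 defines the primary endpoint as "12-month survival. Death, whatever the recorded cause, will be considered as the primary endpoints". Section 6.2 estimates mortality by Kaplan-Meier over 12 months of follow-up and adds: "The survival rate will be compared using the log-rank test".

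**The concern.** Section 3.3 prints nearly everything a power calculation needs, and sections 6.1 and 6.2 supply the test and the horizon. Put together, they do not give 85%. With half of 160 patients expected to die within the year, there are too few deaths for that power at this effect size.

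This is the primary endpoint, and power is what a non-significant result is read against. A reader told that power was 85% will take a null result as fair evidence against a 20-point survival benefit. If power was about 70%, the same result is much weaker evidence.

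**Working it through.** **Inputs.** 80 per group, 1:1 (sections 3.1 and 3.3); 12-month survival 0.40 and 0.60 (3.3); two-sided test (2 and 3.3); levels 0.01 at 70% information and 0.043 at the end (3.3); 10% dropout at 12 months (3.3); log-rank test over 12 months (6.2). Assumptions added here: proportional hazards with exponential survival, and dropout spread over the year at a constant rate.

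**Step 1. Hazard ratio.** ln(0.60)/ln(0.40) = 0.5108/0.9163 = 0.557, so |ln HR| = 0.584.

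**Step 2. Expected deaths within 12 months.**
- No dropout: 80 × 0.60 + 80 × 0.40 = 48 + 32 = 80.
- With a dropout hazard of −ln(0.9) = 0.105, deaths per group are 80 × λ/(λ + 0.105) × (1 − S × 0.9), where S is 12-month survival and λ = −ln S. Placebo: 80 × 0.897 × 0.64 = 45.9. Rifaximin: 80 × 0.829 × 0.46 = 30.5. Total 76.4.
- If the 10% who drop out contributed nothing: 72.

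**Step 3. Deaths needed for 85% power (Schoenfeld).** D = 4(z_α + z_β)²/(ln HR)².
- Level 0.05: 4 × (1.960 + 1.036)²/0.3414 = 105.2, so 106.
- Level 0.043: 4 × (2.024 + 1.036)²/0.3414 = 109.7, so 110.

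Freedman's formula gives 112 and 117. A two-proportion test needs 111 per group at 0.05 and 116 at 0.043, before any allowance for dropout.

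**Step 4. Power of the stated design.** Schoenfeld: Φ(√(D/4) × |ln HR| − z_α). For 76.4 deaths at 0.043: √19.1 × 0.584 − 2.024 = 0.53, and Φ(0.53) = 70.2%.

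| Two-sided, 12-month horizon | Level 0.05 | Level 0.043 |
|---|---|---|
| Log-rank, Schoenfeld, 80 deaths | 74.3% | 72.2% |
| Log-rank, Schoenfeld, 76.4 deaths | 72.4% | 70.2% |
| Log-rank, Schoenfeld, 72 deaths | 69.8% | 67.6% |
| Log-rank, Freedman, 80 deaths | 71.9% | 69.8% |
| Log-rank, Freedman, 76.4 deaths | 70.0% | 67.7% |
| Two proportions, pooled, 80 per group | 72.0% | 69.7% |
| Two proportions, pooled, 72 per group | 67.3% | 65.0% |

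Continuity-corrected two-proportion formulas give less (58.5% to 66.3%).

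The full two-look plan (0.01, then 0.043) was also simulated with the log-rank test cut off at 12 months, 20,000 runs. It gives 70.5% power with dropout and 72.0% without, so the interim look barely changes the answer.

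**Step 5. Where 85% could come from.**
- One-sided 5% test, no dropout, no interim: 81.7% (pooled proportions) to 83.4% (Schoenfeld). Both statements of the claim specify a two-sided test.
- Everyone followed to a common closing date, after 48 months of accrual plus 12 months, with 10% yearly dropout: about 119 deaths. Fixed-sample power is 87% to 89%, and two-look power 86% to 88%.
- Every patient followed for 24 months with 10% yearly dropout: 109 deaths, 86% at 0.05 and 85% at 0.043.

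The last two count deaths after month 12.

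**Step 6. What 160 patients can detect with 85% power.** Take mortality of 60% against 36%. The hazard ratio is ln(0.64)/ln(0.40) = 0.487, and expected deaths with dropout are 73.4. Then √18.3 × 0.719 − 2.024 = 1.06, a power of 85.5% at 0.043. At 37% mortality it falls to 82%.

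**The case against.** The strongest reply is that the SAP does not print the accrual and follow-up times entered in the sample-size software. A standard two-sided log-rank calculation with longer follow-up does reach about 85%, and some passages look beyond a year: treatment to the study end date (section 3.1), safety evaluation to the study end date (6.4) and month-18 stool samples (6.1 and 6.2). The 85% may therefore be a correct answer to a different question, not a slip of arithmetic. That stands as far as origin goes, which this document cannot settle. It does not restore the figure. Sections 6.1 and 6.2 limit the primary endpoint and its analysis to 12 months, section 3.5 ends the trial with the last 12-month visit, and section 3.3 counts interim information as patients with complete follow-up (0.70 × 160 = 112), which fits a fixed horizon per patient.

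Second, the lowest values in the table are too pessimistic for this plan. Sections 5.2 and 6.3 censor withdrawn and lost patients, so they contribute until they leave, and the planned test is log-rank rather than a comparison of proportions. This is right, and it is why the conclusion centres on 70% and not on 65%.

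Third, sections 3.4 and 4.1 speak of the interim as already performed, so the design can hardly change, and the reported hazard ratio with its confidence interval will show the precision actually achieved. This limits the harm to interpretation, but it is no reason to leave a wrong power in the plan from which the trial will be reported.

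**Conclusion.** The concern holds. With follow-up limited to 12 months, the stated inputs give about 70% power under the two-look plan with 10% dropout. The range over standard formulas without continuity correction, levels of 0.05 or 0.043 and dropout treatments is 65% to 74%. The shortfall against 85% is about 15 points and never less than about 11. The type II error is about 30% instead of 15%. The design expects about 76 deaths, some 30 fewer than the 106 to 110 that 85% power requires.

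The hazard ratio rests on proportional hazards, and the figure of 76 deaths on exponential survival with evenly spread dropout. Neither drives the conclusion: the two-proportion calculation needs neither assumption and gives 72.0% at best.

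**What to change.** - In section 3.3, replace the 85% with about 70% power for 12-month mortality of 60% against 40%, naming the log-rank test, the 12-month horizon, the 0.01 and 0.043 boundaries and the 10% dropout.
- Add the expected number of deaths (about 76) and the difference detectable with 85% power (about 60% against 36% mortality).
- In section 2, change the type II error from 15% to about 30%.
- Record the change, dated, in the revision control table with the original 85%, so that the design history stays visible. If the software inputs show a longer follow-up, say so there.

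The cost is SAP wording only. No enrolment, endpoint, test or boundary changes, though the stated power becomes less favourable.

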# **Section 4: Statistical Principles**

# 4.1 Confidence Intervals and P-values

The interim analysis was performed when about 70% of the expected information is available (112 patients with complete follow-up), with a significance boundary p-value of 0.01. Consequently, the final analysis will have to be performed with a significance boundary **p-value of 0.043**.

All other tests will be two-sided, with p values of 0.05 or less denoting statistical significance. 95% confidence interval will be used to report effect estimates of secondary endpoints.

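### The interim information fraction of 70% is a headcount (112/160), while the primary log-rank test's information is deaths; the interim data set is not stated, and the overall alpha of 0.048 does not follow from 0.01 and 0.043 at 70% or later

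*SAP*

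**What the plan says.** SAP 3.3 sets the interim analysis "when about 70% of the expected information is available (112 patients with complete follow-up"), with a boundary of p = 0.01, a final boundary of p = 0.043 and an estimated overall alpha of 0.048. Sections 3.4 and 4.1 repeat the 70% and the 112 patients, and describe the interim in the past tense. Section 4.1 derives the final level from the timing of the look: "Consequently, the final analysis will have to be performed with a significance boundary" of 0.043.

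The design inputs are a "projected 40% survival rate at 12 months in the placebo group and 60% in the rifaximin group", "a dropout rate of 10% at 12 months", and, on size, "We calculated that 160 patients (80 per group) would yield an 85% power in a two-sided test of hypothesis". The Introduction adds: "The inclusion period will be 48 months and 17 centers will participate". For the primary comparison, section 6.2 states: "The survival rate will be compared using the log-rank test".

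The SAP gives no number of deaths for either analysis. It does not define complete follow-up, and it does not say whether the interim test used only those 112 patients or everything recorded by the cut-off.

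**The concern.** In a group-sequential log-rank design, the correlation between the interim and final statistics is the square root of the information fraction, and that fraction is deaths at the look divided by deaths at the end. A patient count is a substitute that can differ from it. By the time 112 patients have finished 12 months, later entrants have already been followed in part and some have died. If those deaths entered the interim test, the look was later on the information scale than 70%.

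The fraction feeds two stated results: the final level that the primary p-value must meet, and the overall false-positive rate that the SAP reports. If it is wrong or undefined, neither can be verified. A late look also fits poorly with the aim in section 3.3 of finding a benefit early in the trial.

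**Working it through.** **Inputs.** From SAP 3.3: 12-month survival 40% and 60%, dropout 10%, 160 patients. From 3.1: allocation "in a 1:1 ratio and stratification on the center". From the Introduction: 48 months of inclusion. My assumptions, not in the SAP: uniform accrual (160/48 = 3.33 patients a month) and exponential times to death and dropout.

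**The plan's own figure.** 112/160 = 0.70 exactly, as a headcount.

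**Expected deaths at the end.** Monthly hazards are −ln(0.4)/12 = 0.0764 (placebo), −ln(0.6)/12 = 0.0426 (rifaximin) and −ln(0.9)/12 = 0.0088 (dropout). With death hazard λ and dropout hazard δ, the probability of an observed death within u months is λ/(λ+δ) × [1 − exp(−(λ+δ)u)]. At u = 12 this gives 0.574 × 80 = 45.9 and 0.381 × 80 = 30.5, so 76.4 deaths in total.

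**One case by hand.** The 112th patient reaches 12 months at 12 + 112/3.33 = month 45.6, when 45.6 × 3.33 = 152 are enrolled. The first 112 contribute 0.70 × 76.4 = 53.5 deaths. The other 40, partly followed, contribute 10.9. The total is 64.4, and 64.4/76.4 = 0.84. Confined to the first 112, the fraction is 53.5/76.4 = 0.70.

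**All readings of the trigger, if all accrued data are used (10% dropout).**

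| 112 patients who have… | Month | Enrolled | Deaths | Fraction |
|---|---|---|---|---|
| died, dropped out or reached month 12 | 41.8 | 139 | 58.4 | 0.76 |
| died or reached month 12 | 44.7 | 149 | 63.0 | 0.82 |
| 12 months elapsed since entry | 45.6 | 152 | 64.4 | 0.84 |
| 12 months elapsed, net of 10% dropout (112/0.9 = 124.4 entered) | 49.3 | 160 | 70.2 | 0.92 |

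Without dropout the first reading gives 0.77. A true 70% of deaths (53.5) would be reached near month 39, with about 129 enrolled. Shapes with more early mortality (Weibull 0.5 and 0.7) give about 0.78-0.93; accrual over 24 to 60 months gives about 0.75-0.96.

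**Overall alpha.** For two-sided boundaries p1 and p2, overall alpha = 1 − P(|Z1| < c1 and |Z2| < c2), where the statistics are bivariate normal with correlation √t. For p1 = 0.01 and p2 = 0.043, c1 = 2.576 and c2 = 2.024. The last column is the final level that would bring the total to 0.05, with 0.01 kept at the interim.

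| t | Overall alpha of 0.01/0.043 | Final level for total 0.05 |
|---|---|---|
| 0.50 | 0.0479 | 0.0452 |
| 0.70 | 0.0456 | 0.0477 |
| 0.77 | 0.0447 | 0.0485 |
| 0.84 | 0.0439 | 0.0493 |
| 0.92 | 0.0432 | 0.0499 |

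The stated 0.048 is not reproduced at 0.70 or later; it fits t of about 0.5.

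**Power of the final test.** The hazard ratio is ln(0.6)/ln(0.4) = 0.557, and the drift is √76.4/2 × |ln 0.557| = 2.554. Power is 70.2% at 0.043, 71.7% at 0.0477, 71.9% at 0.0485 and 72.3% at 0.0499. Moving from 0.043 to the level attainable at t = 0.70 gains 1.5 points. Moving on from there to t = 0.77-0.92 gains about 0.2 to 0.7 point.

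**The case against.** The strongest reply is that the parenthesis describes the interim data set: the first 112 patients, each with 12 months elapsed. They carry 70% of the expected deaths, the dropout rate cancels, and the stated fraction is right. This stands as a possible reading. A reader might infer that the look was certainly not at 70%; the SAP does not support that, because it does not exclude this restriction. It does not state it either, and the restriction would mean leaving out deaths already recorded in later patients.

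A reader might also take 112/144 = 78% as the fraction, on the ground that only 144 patients are expected to finish. That is not a log-rank information fraction. It ignores deaths, and sections 5.2 and 6.3 keep withdrawn patients in the analysis, censored.

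A third reading is that 0.043 was calibrated to a 70% look and is wrong only because the look came later. The numbers do not fit that. At t = 0.70 the level for a total of 0.05 is already 0.0477, and 0.048 matches a look near the halfway point. Most of the gap therefore has another origin, and it would be wrong to charge the full 2 points of power to the fraction.

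Finally, validity is not harmed. Section 3.3 promises an overall risk below 0.05, and that holds at every fraction examined. A later look makes the fixed pair more conservative.

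**Conclusion.** The point holds as a defect of definition and of one reported figure, not as a threat to validity. The SAP measures information in patients for a test whose information is deaths, and leaves the interim data set unstated. The fraction is 0.70 under one reading, and about 0.76-0.92 if all accrued data were used, with 139-160 of 160 enrolled. The second range rests on uniform accrual over 48 months and exponential times; other shapes and accrual lengths change its size but did not bring any all-data case down to 70%.

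The overall alpha of 0.048 is wrong at all of these fractions. The true value lies between about 0.043 and 0.046. The final test is slightly conservative, and the part due to the fraction is well under one point of power.

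**What to change.** In SAP 3.3, 3.4 and 4.1:

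- State which patients' data entered the interim test, and define complete follow-up.
- Give the information fraction as deaths in the interim test divided by deaths at the final analysis, both pooled over arms.
- Leave the 0.01 used at the interim unchanged.
- Before final unblinding, take one of two routes. Either keep 0.043 and restate the fraction and its overall alpha (about 0.043-0.046, not 0.048), or recompute the final level from the observed fraction for a total of 0.05 (about 0.048-0.050).

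The cost is some SAP wording and one boundary calculation from pooled death counts, with no new data or patients. The second route relaxes a prespecified threshold after the interim has been done, so it must be documented and justified. Since the fraction accounts for so little power, keeping 0.043 with a corrected alpha is the least contentious choice.

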### 3.4 Statistical Interim analyses and stopping guidance

One interim analysis was performed when 70% of the expected information will be available (112 patients with complete follow-up). The critical p-value was set at 0.01.

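### SAP section 3.3: t² spending, a look at about 70% information, the boundaries 0.01/0.043 and an overall alpha of 0.048 do not fit together; the rule is conservative, but its stated basis needs reconciling

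*SAP*

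**What the plan says.** Section 3.3 of the SAP names the method as a "flexible alpha spending function (specifically alpha time (t2) spending function") and says that it keeps the overall risk below 0.05. It then gives four figures:

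- Timing: "The interim analysis will be performed when about 70% of the expected information is available (112 patients with complete follow-up"), which is 112/160 = 0.70.
- Interim boundary: p = 0.01, repeated in section 3.4: "The critical p-value was set at 0.01".
- Final boundary: "Consequently, the final analysis will have to be performed with a significance boundary p-value of 0.043". Section 4.1 repeats this value.
- Overall risk: "The estimated alpha nominal risk using these critical values will be 0.048".

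The test is two-sided. Section 6.2 fixes the primary test: "The survival rate will be compared using the log-rank test". Sections 3.4 and 4.1 speak of the interim analysis in the past tense, so the interim boundary appears to have been applied already.

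**The concern.** The spending function, the information fraction and the total alpha together determine both boundaries. A reader can therefore check the SAP's chain from its own inputs, and the check fails at two points. The named function at the named fraction does not give 0.01 and 0.043, and that pair at that fraction does not give 0.048. The link from 0.01 to 0.043, which section 3.3 presents as a consequence, does not follow at 70% either.

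What is at stake is the documented basis of the primary decision threshold and the stated type I error. A reader who recomputes the boundary from the named method gets 0.0394. A final p-value between 0.0394 and 0.043 could then invite a dispute over which threshold the SAP supports. A report that repeats section 3.3 would carry the mismatch into print.

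**Working it through.** **Inputs, all from the SAP.** Spending function alpha·t², look at t = 0.70, boundaries p₁ = 0.01 and p₂ = 0.043, stated overall alpha 0.048, two-sided, two looks (section 3.3); log-rank test (section 6.2). The total alpha to be spent is taken as 0.05, with 0.048 as a variant.

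**Model.** Two standardised statistics with correlation √t. Overall alpha = 1 − P(|Z₁| < c₁ and |Z₂| < c₂), where c₁ = 2.576 (p = 0.01) and c₂ = 2.024 (p = 0.043). At t = 0.70 the correlation is √0.70 = 0.837.

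**Step 1: boundaries from the stated method.** Alpha spent at the interim is 0.05 × 0.70² = 0.05 × 0.49 = 0.0245. Solving for the final level that brings the total to 0.05 gives 0.0394. With a total of 0.048 the pair is 0.0235 and 0.0377. Neither is 0.01/0.043, and the interim gap (0.0245 against 0.01) is too large for rounding.

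**Step 2: overall alpha of the stated pair at 70%.** The two levels sum to 0.053. The probability of crossing both boundaries under the null is 0.0074, so overall alpha = 0.053 − 0.0074 = 0.0456. Rounding of the printed thresholds (0.0095 to 0.0105 and 0.0425 to 0.0435) moves this between 0.0449 and 0.0462, which does not reach 0.048.

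**Step 3: does 0.043 follow from 0.01?** After 0.01 at t = 0.70, a final level of 0.0477 would bring the total to 0.05, and 0.0456 would bring it to 0.048.

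**Step 4: where the printed figures do fit.** Varying only the look time:

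| t | total | t² boundaries | overall alpha of 0.01/0.043 |
|---|---|---|---|
| 0.45 | 0.048 | 0.0097 / 0.0427 | 0.0485 |
| 0.50 | 0.05 | 0.0125 / 0.0436 | 0.0479 |
| 0.70 | 0.05 | 0.0245 / 0.0394 | 0.0456 |

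The pair 0.01/0.043 has an overall alpha of exactly 0.048 at t = 0.49. At t = 0.45 with total 0.048, the t² boundaries round to the printed pair. So 0.01, 0.043, 0.048 and the named function agree, to rounding, at about 45 to 50% information, and not at 70%.

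**Step 5: other spending functions at t = 0.70, total 0.05.** Linear gives 0.035/0.030, t^1.5 gives 0.0293/0.0354, t³ gives 0.0172/0.0442, O'Brien-Fleming type 0.0148/0.0455 and Pocock type 0.039/0.024. None gives 0.01/0.043.

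**Step 6: log-rank simulation under the null** (80 per arm, interim on the first 112 patients, exponential survival). With 10% dropout and 600,000 trials per setting, overall alpha is 0.0455 to 0.0468. A second set, with and without dropout and 200,000 trials per setting, gives 0.0461 to 0.0471.

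**Step 7: sensitivity to the information fraction.** Log-rank information is the number of deaths, and the SAP does not give the fraction of deaths at the interim. Assuming a range, the normal model gives:

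| death fraction | 0.65 | 0.70 | 0.75 | 0.80 | 0.84 | 0.90 |
|---|---|---|---|---|---|---|
| overall alpha | 0.0462 | 0.0456 | 0.0450 | 0.0444 | 0.0439 | 0.0433 |

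If patients still in follow-up also counted at the interim, and accrual was even over the 48 months in the SAP introduction (an assumption), the death fraction averages about 0.84 and simulated alpha is about 0.0445 to 0.0449.

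**The case against.** Four points can be made for the SAP.

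1. *The figure 0.048 is called an estimate and may come from a simulation.* Section 3.3 names the software but no run count. Assuming 2,000 to 20,000 runs, the 95% margin is about 0.009 to 0.003, which covers the distance from 0.0468 to 0.048. This stands in part: the 0.048 limb is the weaker one. It does not repair 0.0245 against 0.01, which is plain arithmetic.

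2. *The design calculation may have used a test of two proportions.* Section 3.3 states 12-month survival rates, counts patients with complete follow-up and does not name the test used for the design. For 56 then 80 per arm and null rates of 0.4 to 0.6, the exact overall alpha of a two-proportion z-test is 0.0465 to 0.0503, a range that contains 0.048. That is a possible origin for the number, but section 6.2 applies these thresholds to a log-rank test, and the spending mismatch is the same for either test.

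3. *The t² statement may be true and only the 70% wrong.* Step 4 shows that this is possible. It does not make the section consistent, but it means the t² claim should not simply be deleted as the error.

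4. *Nothing in the trial's decisions changes.* This stands, and it sets the severity.

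A reader might also infer that type I error is inflated, or that the final threshold ought to be 0.0394. The SAP supports neither. The overall alpha of 0.01/0.043 is below 0.05 at every death fraction considered, and the two thresholds are stated explicitly and repeated consistently in sections 3.3, 3.4 and 4.1.

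**Conclusion.** The point holds as an internal inconsistency of low severity. At the stated 70%, t² spending gives 0.0245/0.0394 and not 0.01/0.043, and the stated pair has an overall alpha of about 0.046 and not 0.048. That is a difference of 0.048 − 0.0456 = 0.0024 in the safe direction in the normal model, and about 0.001 to 0.002 against the log-rank simulations. Either the look time used in the calculation or the named derivation is misstated. That the thresholds were computed for a look near half information is a plausible inference, but the SAP does not show it.

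The boundary result rests only on the SAP's own inputs and a total alpha of 0.05 (or 0.048). The overall alpha rests on the two-look normal model at an information fraction of 0.70. The true fraction of deaths at the interim is not stated, and a larger one lowers the overall alpha further. The rule is conservative.

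**What to change.** Before unblinding, amend section 3.3 as follows:

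- Keep 0.01 and 0.043 as fixed, prespecified boundaries. They should be neither tightened to match t² at 70% nor relaxed to use up the remaining alpha.
- Retrieve the design calculation and state the spending function, total alpha and information fraction that actually produced the boundaries. If the look was moved after the calculation, or the boundaries were chosen directly, say so.
- Restate the overall alpha for the log-rank test at the fraction of deaths actually reached at the interim: about 0.046 at 0.70, and 0.046 to 0.043 for fractions from 0.65 to 0.90.

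The cost is SAP wording and one count of interim deaths. The sample size, the thresholds and the analysis do not change.
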